### **Vigabatrin and Placebo:**

The investigational drug product to be used in this study is vigabatrin, marketed in the US under the trade name Sabril by Lundbeck Pharmaceuticals. Lundbeck will supply vigabatrin for this study directly to the Investigational Pharmacy at Cincinnati Children's Hospital (CCHMC). It is supplied as a white granular powder enclosed in 50x60 mm child-resistant aluminum foil packets (sachet). It is non-hygroscopic, freely soluble in water, and thermodynamically stable with an established shelf life of more than 36 months at room temperature. Povidone is the primary inactive excipient. The investigational pharmacy at CCHMC will produce identical white granular powder with indistinguishable

physical appearance, color, solubility, and taste to the vigabatrin powder supplied by Lundbeck. Both vigabatrin and placebo will be repackaged into identical aluminum foil sachets so as to maintain treatment blinding and distribute as appropriate to the investigational pharmacies at local participating sites for individual patient distribution and administration. For administration, the entire content of one sachet (500 mg active drug) is dissolved in 10 ml water for oral administration that is dosed according to body weight 50-150 mg/kg/day divided BID. Dosing will follow established recommended guidelines (50 mg/kg/day and increased as needed by 50 mg/kg/day every 3 days up to a maximum dose of 100 mg/kg/day, divided BID in the blinded phase and 150mg/kg/day in the Open Label Phase).

Subjects randomized to vigabatrin in Arm A (Figure 1) will be treated with vigabatrin 100mg/kg/day or placebo until 24 months of age or until they show evidence of clinical seizures or electrographic seizures on video EEG. Based on the published EEG biomarker data for infants with TSC, the subjects randomized to our primary randomized trial population, Arm A (who have evidence of epileptiform activity in their EEG) will be at high risk for developing epilepsy (approaching 100%).

If the subjects in Arm A are seizure free at 24 months of age, they will be tapered off the study drug (vigabatrin or placebo) without breaking the treatment blind and continue to be followed for the duration of the study (36 months).

If electrographic or clinical seizures occur while on study drug, they will transition into the Open label phase of the study (Arm B) and continue to be followed until 36 months of age as per the PREVeNT protocol schedule. If the seizures are not controlled in the Open label phase at the vigabatrin maximum dose of 150mg/kg/day, the investigator may change the antiepileptic medication as clinically warranted to improve seizure control (including tapering off vigabatrin). These subjects will remain in the open arm of the study for the duration of the protocol (36 months).

Based on the TSC-EBS data, it is estimated that 30% of subjects (24 subjects) in Arm C will not be treated but continue in the study until the age of 36 months (Table 2).

See Pharmacy Manual for details of packaging and labeling, product tracking and accountability, and product disposal and destruction.

### **Developmental Assessments:**

The developmental leadership team will oversee the implementation of the developmental assessments and monitor the quality and consistency across all sites.

All enrolled subjects, regardless of which arm of the PREVeNT protocol, will complete the Bayley-III assessment scale and Vineland -II (Survey Interview Form), at 6 months, 12 months, 24 months and 36 months of age. The Bayley Social Emotional Adaptive Behavior Assessment will be completed at the 6 month study visit. The Bayley Scales of Infant and Toddler Development, Third Edition (Bayley-III) which will be completed at 12,

24 and 36 months of age. The blind will be maintained for the clinical psychologist performing the developmental assessments throughout the study. They will be blind to treatment arm, subject's seizure control and concomitant medications. In addition to the primary outcome analysis to determine the impact of early vs. delayed treatment with vigabatrin on neurodevelopmental outcome at 24 months, the inclusion of the 12-month time-point allows additional exploratory analysis to determine if problematic areas of cognitive function and/or developmental domains are evident before 24 months of age. Additional developmental assessments will be completed which include the subdomain scores of the Bayley-III, Vineland (Survey Interview Form), Beery Visual Motor Integration (VMI), Child Behavior Check List (CBCL) and ADOS2, and/or Brief Observation of Symptoms of Autism (BOSA)\* and DSM-5 checklist at 24 months. At 36 months of age subjects will complete the same assessments as 24 months with the addition of the BOSA\* and ADI-R if the ADOS is not administered, as an exploratory analysis to assess whether changes observed at 24 months are consistent with those seen at 36 months and indicative of long-term outcome and those subjects at risk for autism or ASD. At 36 months of age subjects will also complete the Peabody Picture Vocabulary Test (PPVT). When appropriate instruments are available, measures can be administered to Spanish speaking individuals.

\*During the COVID-19 Pandemic and for the remainder of the study the BOSA and DSM5-checklist was added to the 24 and 36 month study visit. This would enable the study to complete the Autism assessments at the 24 and 36 month visit using a valid assessment tool while complying with the COVID-19 safety measures. Because of the requirement to wear a facemask during the subject's study visit would invalidate the ADOS-2 result. In its place the BOSA will be administered over a 15-20 min session by trained ADOS-2 research reliable psychologists, since it requires the same clinical skill and judgement required for the ADOS-2 administration and scoring. The ADI-R will be completed at the 36 month study visit if the ADOS is not administered to aid the Autism diagnostic accuracy with the BOSA. (See Appendix 3 page 36)

A summary of the neurodevelopmental assessment will be provided to the site investigators after each assessment. If the subject shows evidence of developmental delays they will be referred for early intervention services, including physical, occupational and speech therapy. The investigators are aware that this could potentially bias the results but it is ethically imperative that referrals to early intervention services be initiated when warranted. The proportion referred and the early intervention services implemented will be tracked over the duration of the study

### **Ophthalmologic Assessments:**

Since approval of vigabatrin for the treatment of infantile spasms in 2009, the FDA has required a risk evaluation and mitigation strategy (REMS) that includes recommended ophthalmologic evaluations every 3 months. For the current study, this recommended safety guidelines of the REMS program will be followed, but we recognize that this creates some unique challenges within a double-blinded, placebo-controlled randomized study. All subjects enrolled in the PREVeNT Trial will follow a standard ophthalmologic protocol.

At each site, the ophthalmologic examination will be completed by a pediatric ophthalmologist or neuro-ophthalmologist who has experience in TSC infant ophthalmologic examinations.

The protocol will include a baseline eye exam within 4 weeks of initial enrollment in study. This will include: visual acuity, pupillary reaction and dilated funduscopy examination with fundus photography. Electroretinography (ERGs) will **not** be obtained as part of the ophthalmologic examination at any of the participating sites. It should be noted that the FDA risk evaluation and mitigation strategy (REMS) program does not require ERGs.

Subjects randomized to the Blinded Treatment phase (Arm A) will be treated with vigabatrin 100mg/kg/day or placebo until 24 months of age, or have a clinical seizure or electrographic seizure on EEG as determined by the Central EEG Reader. During this phase of the study, the established FDA REMS guidelines will be followed. Eye examinations will be completed within 4 weeks after randomization (Arm A) and then every three months while the subject is in the double blind phase of the study. The eye exams will include: visual acuity, pupillary reaction and dilated funduscopy examination. A final eye exam will be completed after the subject has been off study drug for 3-6 months. The final exam will include: visual acuity, pupillary reaction and dilated funduscopy examination.

If the subject continues into the Open-label phase (Arm B) of the study and remains on vigabatrin, the REMS guidelines will be followed as long as they are treated with vigabatrin. A final eye exam will be completed once they have been off vigabatrin 3-6 months in the Open label phase of the study. The final exam will include: visual acuity, pupillary reaction and dilated funduscopy examination with fundus photography.

If the subject remains in Arm C (seizure free and Normal EEG) they will have a baseline eye exam within 4 weeks of the initial enrollment in the study. A repeat eye exam will be done at 12 months of age, 24 months of age and 36 months of age.

If at any time during the study the ophthalmologist detects visual changes in the subject, they will contact the site PI directly. At that point, the site PI and ophthalmologist will discuss and recommend further ophthalmologic assessments such as Pediatric optical coherence tomography (OCT) under anesthesia and fundus photography. The parents/LAR, examining ophthalmologist, site PI, and NIH DSMB will review the ophthalmologic examination results and consider all options including the decision to withdraw from the study at that point.

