Pupils	Irregular shape, anisocoria, afferent defect	X	X
Visual acuity Fix and follow	Failure to fix and follow, failure to maintain central fixation	X Cooperative infant 3 months or older	X
Corneal reflex	Asymmetric or displaced	X	X
Retinoscopy & Strabismus	Significant Myopia, hyperopia Anisometropia	Glasses & amblyopia therapy at discretion of the pediatric ophthalmologists	X
Dilated funduscopic examination	Retinal hamartomas Optic atrophy Photos if possible	X	X

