Additional developmental measures and ASD Risk: The sub-scores on the Bayley-III and the composite score estimated using Hotelling’s  $T^2$ . The power for this endpoint will vary, but is expected to be similar to the primary. In the children with Pervasive Developmental Disorders, the effect sizes versus normal matched controls were 1.77, 1.67, 1.17 and 1.33 for the Receptive communication, Expressive Communication, Fine and gross motor sub-scores respectively. The ADOS2 will be completed at 24 and 36 months of age as a neurodevelopmental assessment for symptoms of ASD. The results from Study Arm A (seizure free, no treatment), Arm B (VGB versus. Placebo), and subjects with electrographic seizures at baseline EEG who move directly into Open Label treatment will be compared increasing our power to assess differences (Figure1).

Determination of vigabatrin safety as a preventative treatment for clinical seizures in infants with TSC will be assessed using comparison between the treatment groups and as a summary of exposure time on the drug. The outcome measure will be percentage of patients in each group (vigabatrin early treatment vs. vigabatrin delayed treatment) with treatment associated adverse events (AEs), serious adverse events (SAEs), and risk evaluation and mitigation strategy (REMS) measures. Treatment related AEs and SAEs will be monitored and tabulated. Given the expectation that the delayed group will cross-over to active treatment sooner than the early treatment group, adverse events will be characterized using life table approaches to ensure adjustment for exposure time. Thus, counts of individuals with AEs, total number of specific AEs and rate per months of follow-up will all be provided and assessed for any differences and for the safety population (early plus late on person years of exposure basis). Events of specific interest and risk evaluation and mitigation strategy (REMS) measures will be compared, including any and all ophthalmologic problems that may arise. Data from the negative control group (estimated to be approximately 15-20 patients) will also be used to compare the occurrence of AEs and SAEs.

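### The final eye exam lists fundus photography in open label but not in the blinded arm, so eye findings could be ascertained differently in the early and delayed groups

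*Combined protocol and SAP*

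**What the plan says.** Under Ophthalmologic Assessments, every enrolled child has a baseline exam: "This will include: visual acuity, pupillary reaction and dilated funduscopy examination with fundus photography". The final exams differ by phase.

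- **Blinded arm (Arm A):** the final exam follows when the child has been "off study drug for 3-6 months. The final exam will include: visual acuity, pupillary reaction and dilated funduscopy examination". Photography is not listed.
- **Open label (Arm B):** "The final exam will include: visual acuity, pupillary reaction and dilated funduscopy examination with fundus photography". Its timing is conditional: "A final eye exam will be completed once they have been off vigabatrin 3-6 months in the Open label phase of the study".

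The same section opens its protocol with "All subjects enrolled in the PREVeNT Trial will follow a standard ophthalmologic protocol". The table of age-appropriate methods, in the vision-testing background, puts "Photos if possible" beside dilated funduscopy and does not distinguish arms. Table 1, note 1, gives only the timing of the final exam, so it does not settle the content.

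The safety paragraph of the Analyses section compares events of interest and REMS measures between the early and delayed groups, "including any and all ophthalmologic problems that may arise". It adjusts for exposure time but has no rule for unequal exam content.

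**The concern.** A child on study drug enters open label because a seizure occurred. That is the event early treatment is meant to prevent, so the final exam a child is due depends on a post-randomization outcome that the plan expects to differ sharply between groups. Children who stay seizure free on early vigabatrin have the longest preventive exposure, yet no final photograph is listed to set against their baseline one.

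Secondary objective 3 is to confirm the safety of preventive vigabatrin, and vision is the main concern named in the rationale. The vision-testing background also stresses comparison with baseline, since it reports that 20-40% of candidates for vigabatrin already have afferent visual abnormalities. If the two exams differ in what they can reveal, part of any difference between groups in eye findings could reflect the exam rather than the drug.

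**Working it through.** **1. Inputs.** The sample-size text under Primary Study Objective assumes 24 children per group. Seizure proportions are 22/24 = 0.917 on placebo (delayed) and 5/24 = 0.208 on vigabatrin (early), with a less favourable 10/24 = 0.417 for early.

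**2. The plan's own figures.** Full enumeration of the two-sided Fisher exact test at 0.05 with 24 per group gives:
- 0.917 v 0.208: power 99.98% (stated 99%)
- 0.917 v 0.417: power 96.3% (stated above 90%)

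The rates are used below only to count children per phase.

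**3. Who reaches the phase whose final exam lists photography.**
- Delayed: 22/24 = 92%
- Early: 5/24 = 21%, or 10/24 = 42%
- Gap: 17/24 = 71 points, or 12/24 = 50 points

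Children finishing in the blinded arm number 24 − 5 = 19 early and 24 − 22 = 2 delayed, so 19/21 = 90% are early. In the less favourable case there are 14 and 2, and 14/16 = 88% are early.

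**4. Why these are upper figures.** The open-label final exam needs 3-6 months off vigabatrin, and no planned stopping date for open-label vigabatrin is given. Follow-up ends at 36 months, so a child still on drug after month 36 − 3 = 33 cannot reach that exam within the study.

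**5. Possible effect of photography on counts (illustration).** The documents give no detection rates. I assume:
- an equal true rate r of 10-15% in both groups, borrowing the rationale's range for visual field loss;
- a gain in detection d from photography of 0.20 (70% to 90%) or 0.30 (50% to 80%);
- a fraction f of 25-100% of open-label children reaching the off-drug exam, the same in both groups.

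Apparent excess in the delayed group = r × d × gap × f.
- Largest: 0.15 × 0.30 × 0.708 × 1 = 0.032, or 3.2 points; × 24 = 0.77 child
- Smallest non-zero: 0.10 × 0.20 × 0.50 × 0.25 = 0.0025, or 0.25 point; × 24 = 0.06 child
- With d = 0, or with photographs taken at all final exams: zero

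**6. Why the direction is not certain.** Now count children who have any off-drug final exam, supposing that all blinded-arm finishers attend theirs. Early = 19 + 5f and delayed = 2 + 22f.
- f = 0.5: 21.5/24 = 90% early, 13/24 = 54% delayed
- f = 0.25: 20.25/24 = 84% early, 7.5/24 = 31% delayed

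In the less favourable case early = 14 + 10f, giving 19/24 = 79% and 16.5/24 = 69%, against the same delayed figures. So the early group could have fewer photographs but more complete off-drug examination. Step 5 leaves this out, because it assumes that the other exams detect equally well in both groups.

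**The case against.** The strongest case against is that this is a drafting slip with little consequence. The standard-protocol sentence and the methods table both point to a common exam, and the text is to be converted into an SOP and eCRFs meant to standardize evaluation. Blinded children have eye exams every three months, open-label children on vigabatrin follow REMS, and both final exams include acuity, pupils and dilated funduscopy. Photography or OCT can be recommended for any child in whom visual change is detected. The vision-testing background names acuity, visual fields, funduscopy and OCT as the ways abnormalities were measured, and photography is not among them.

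Most of this stands. It limits the size of the problem and makes inconsistency the likelier explanation. It does not say which description governs, and it gives the analysis no rule if the exams are carried out as listed.

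A reader might go further and infer that the safety comparison is biased and makes preventive vigabatrin look safer. The documents do not support that. No section shows that photography finds harm that funduscopy misses, and the conditional open-label exam could narrow or reverse the difference. The split is also by phase, so early children who seize are due the open-label exam too.

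**Conclusion.** The final-exam descriptions conflict with each other in content, and with the standard-protocol statement and the methods table. As written, the exam due depends on a post-randomization seizure. On the planning rates, 21% to 42% of early children against 92% of delayed children reach the phase whose final exam lists photography.

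The ratios of these shares, 0.917/0.417 = 2.2 and 0.917/0.208 = 4.4, describe who is due a photograph at most. They should not be read as the size of a bias. On the stated assumptions the effect of photography alone is about 0.06 to 0.8 child per 24, and it is zero if photography adds no detection or is done at all final exams.

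The supported conclusion is that ascertainment of eye findings could differ between randomized groups, probably by a small amount and in an uncertain direction. It rests on the assumed seizure rates and on the exams being done as listed. No sample size or power figure is affected.

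**What to change.** **Protocol.** Reconcile the two final-exam descriptions under Ophthalmologic Assessments with the methods table, so that final-exam content is stated once and does not depend on the phase in which a child finishes. The content is for the sponsor to decide. The SOP and eCRFs should follow the reconciled text.

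**Analysis.**
- Base the between-group eye comparison, by randomized group, on change from baseline in the elements scheduled at both final exams as reconciled. If photography is made common to both, it belongs in that comparison.
- List separately any finding seen only on an element that is not common to both.
- Report, per randomized group, how many children had a final off-drug exam and how many were photographed.

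**Cost.** A protocol clarification and a few lines of analysis text. The analysis part needs no added procedure. Its small downside is that findings on non-common elements are left out of the formal comparison, though they are still listed.

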## **PREVeNT Trial Background for Vision Testing and Creation of eCRFs**

### **Background**

The PREVeNT trial will require evaluation of the visual function of patients enrolled in the study because of previous reports of adverse effects of vigabatrin upon the anterior afferent visual system. However, more recent work from the FDA/Lundbeck Risk

Evaluation Mitigation Strategy [REMS] program and the prospective “Lundbeck Vision Study” has disclosed a much lower incidence of visual defects than previously reported in the literature.

The discrepancy between the past studies and the more recent work is explained by obtaining baseline evaluations of the patients eligible for vigabatrin compared to the prior case reports that were cross-sectional in nature and failed to evaluate the patients’ baseline visual status and also failed to account for the now well-recognized high variability of automated visual field testing. Studies by Gonzalez et al; Sergott et al, the REMS reports over the past 6 years since FDA approval and the Lundbeck vision study have consistently demonstrated that 20-40% of patients considered appropriate for vigabatrin therapy have abnormalities of the afferent visual system at baseline as measured by visual acuity, visual fields, fundusoscopic examination and optical coherence tomography [OCT].

Based upon these new data, the REMs program and the product label are now being considered for revisions by the FDA. Although it is premature to assume that vigabatrin is without any risk to the visual system, the current data suggest that it may be safer than originally thought at least over a 24 month cumulative exposure.

The following protocol is being proposed to protect the vision of the subjects participating in the PREVeNT trial. The protocol will then be converted to a standard operating procedures [SOP] format and electronic clinical research forms [eCRFs] to insure that the subjects are evaluated in a standardized manner at all the clinical sites and that the data can be analyzed throughout and at the conclusion of the trial.

Age Appropriate Methods for Evaluation of Visual Function [Based upon the recommendations of the American Academy of Ophthalmology]

Method	Abnormalities	Recommended Age	
		Newborn to 6 months	6 months until Able to cooperate With testing
Red Reflex & Bruckner test	Absent, white, dull opacified, asymmetric	X	X
External Exam	Structural abnormality such as ptosis, proptosis	X	X

Pupils	Irregular shape, anisocoria, afferent defect	X	X
Visual acuity Fix and follow	Failure to fix and follow, failure to maintain central fixation	X Cooperative infant 3 months or older	X
Corneal reflex	Asymmetric or displaced	X	X
Retinoscopy & Strabismus	Significant Myopia, hyperopia Anisometropia	Glasses & amblyopia therapy at discretion of the pediatric ophthalmologists	X
Dilated funduscopic examination	Retinal hamartomas Optic atrophy Photos if possible	X	X

### Optical Coherence Tomography

To be performed if high index of suspicion for decreased visual function. Will require general anesthesia.

#### Examination

1. Documentation of the child's level of cooperation with the examination required to interpret the results
2. Testing of sensory function should be performed before any dissociating techniques such as covering an eye to check monocular visual acuity or cover testing to test ocular alignment. Testing for alignment should be done before dilating drops are instilled.
3. Binocular Red Reflex [Bruckner] Test
  - a. In a darkened room, the direct ophthalmoscope light is directed towards both eyes from approximately 18-30 inches.
  - b. A symmetric red reflex in each eye is normal

- c. Opacities of the reflex are always abnormal
- d. The reflex will vary upon retinal pigmentation so variation will be present by race/ethnicity
- e. Significant hyperopia demonstrates an inferiorly placed brighter crescent in the reflex
- f. Significant myopia presents as superiorly displaced reflex
- g. Also used to assess for ocular misalignment—esotropia, exotropia, and hypertropia.

